11.5 Monitoring of Adverse Events

Every AE must be followed to a satisfactory outcome or stabilization of the event, even when this requires a time period beyond the scope of the study (this is particularly applicable to SAEs). Outcome includes information on recovery and any sequelae, as well as specific tests and/or treatments that may have been required and their results. For

a fatal outcome, cause of death and a comment on its possible relationship to the suspected reaction should be provided.

The terms used to define outcome are as follows (outcome of reaction/event at the time of last observation):

- Ongoing,
- Resolved without sequelae,
- Resolved with sequelae, and
- Death.

Actions taken in response to an AE and follow-up results must be recorded in the subject's medical record (this includes follow-up laboratory results). Any treatment administered for the AE must be recorded in the subject's CRF. When subjects are discontinued from the study due to an AE, relevant clinical assessments and laboratory tests will be repeated as necessary until final resolution or stabilization occurs.

11.6 Reporting of Serious Safety Issues; Suspension Guidelines

Serious safety issues that arise in this study will be brought to the attention of the CSCC Data and Safety Monitoring Board (DSMB), which will make recommendations to the National Heart, Lung, and Blood Institute (NHLBI) regarding possible suspension or termination of the study. The NHLBI will consider the DSMB's recommendations, determine an appropriate action, and notify the Principal Investigator (PI) and the CSCC Statistics and Data Management Center (SDMC). The PI will notify all participating investigators, who will implement the actions directed by NHLBI. This section defines "serious safety issues" and describes procedures for bringing them to the attention of the DSMB.

The SDMC or PI will make the following types of reports that can alert the DSMB to a potential safety issue:

- Ad hoc reports of unexpected SAEs that are made within 7 or 15 calendar days, as specified in subsequent paragraphs.

- Reports of quarterly statistical analyses of all SAEs. The SDMC makes such analyses quarterly, but files a report to the DSMB only when analyses indicate that a safety issue has arisen, as defined by the “alert” criteria.
- Reports of semi-annual SDMC analyses of all AEs and of adverse clinical laboratory trends. These reports will highlight any safety issues revealed by the analyses that meet the “alert” criteria.

11.6.1 Reporting of Serious Adverse Events

SAE reporting will begin with events that arise after the informed consent is signed until 30 days after the last dose of study drug. Within 1 day of the realization that an SAE has occurred to a study subject, a study investigator must make an initial report CSCC Statistics and Data Management Center SAE Regulatory Specialist. The report should describe the event as fully as possible. The initial SAE reports received from the site should include the following minimum information: an identifiable subject; study product; an identifiable reporting source; and an event or outcome that can be identified as serious. Supporting documentation (e.g., CRF pages, lab reports, summary notes, autopsy reports) should accompany the report.

All participating sites will be expected to report fatal or life threatening SAES to their local IRBs according to standard institute guidelines and procedures.

The site investigator, the Medical Monitor, and the SDMC SAE Regulatory Specialist will collaborate to prepare a report of the SAE using the current version of the FDA’s SAE reporting forms. A fatal or life-threatening unexpected SAE will be reported to the DSMB within 7 calendar days of the receipt of the initial report by the SDMC SAE Regulatory Specialist. A non-fatal, non-life-threatening, unexpected SAE will be reported to the DSMB within 15 calendar days of the receipt of the initial report by the SDMC SAE Regulatory Specialist.

The PI will submit the DSMB report to the Chair of the DSMB Subcommittee appointed to monitor this study and to the NHLBI Project Officer. The PI will submit the SAE report to all study investigators. Each study investigator will submit the SAE report to

the local institutional review board (IRB) and other local authorities in accordance with the institution's regulations.

All SAEs, regardless of expected status, are also recorded in the AE section of the study's CRF.

The site investigator will follow the progress of a subject who experiences an SAE until the SAE is resolved or considered stable. When the SAE has not resolved by the report deadline, the site investigator will make follow-up reports in accordance with directions from the DSMB and/or the site's IRB.

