7.1.2 Description of Type of Study

This is a multi-center, randomized, double-blind, placebo-controlled Phase III clinical trial that will include at least 56 subjects with SCD who are hospitalized for ACS. Individuals who meet entry criteria will be randomized to receive either dexamethasone or placebo. Dexamethasone will be administered initially as 0.3 mg/kg by mouth every 12 hours for a maximum of 4 doses (2 days) or until discharge from the hospital, whichever occurs first. Afterward, the study drug will be tapered over 6 days for a total duration of therapy not to exceed 8 days. Due to possible age-related and ACS severity-related differences in the duration of signs and symptoms of ACS, randomization will be stratified by age and severity of ACS (see Section 8.3). We are enrolling a maximum of 112 pediatric subjects. We will enroll adult subjects at the rate site participation will allow, which we anticipate will be no more than 56 subjects. Interim analyses will be performed when a total of 56 subjects and 112 subjects have completed their hospital stay. If we do not stop enrollment after these interim analyses are completed, we will continue to enroll up to a maximum total of 112 pediatric subjects. The efficacy and safety of dexamethasone will be compared to placebo in the context of standard supportive care for ACS.

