9 TREATMENT OF SUBJECTS

9.1 Treatments

9.1.1 Description of Study Drug and Dosing Regimen

Dexamethasone is a commercially available synthetic corticosteroid hormone that is used primarily as an anti-inflammatory agent. It is available in tablets (several manufacturers), and as a solution for IV injection (several manufacturers).

Potential AEs, especially when given chronically, include hypertension, hyperphagia, weight gain, hyperglycemia, striae, acne, osteopenia, personality changes, gastrointestinal ulceration and hemorrhage, and growth retardation. Dexamethasone, like other steroids, may cause avascular necrosis of bone.

The dosing of dexamethasone, or an equivalent amount of placebo, is specified in Table 9.1. The initial dose (0.3 mg/kg every 12H) is given for a total of 2 days (4 doses) or until hospital discharge, whichever occurs first. Note: Time Zero is defined as the initial dose of study drug and the first 24 hour period begins with the first dose. All subsequent doses and study assessments are scheduled from this time point. Afterward, all subjects will receive the taper as specified in Table 9.1. All study drug should be given by mouth. If medications temporarily cannot be given by mouth (e.g. NPO status for a diagnostic test or altered mental status) then the temporary administration of the study drug by vein during this time period is acceptable. The dose of IV study drug is the same as the oral formulation. The study drug should be given by mouth as soon as oral medications can be tolerated.

Table 9.1 Dose and Frequency of Study Drug

Dose (mg/kg)	Max single Dose (mg)	Frequency	24hr dose (mg/kg)	Duration (days)	
0.3	12	Every 12H	0.6	2 (or hospital discharge)	} “High Dose”
0.3	12	Every 24H	0.3	2	
0.2	8	Every 24H	0.2	2	} “Taper”
0.1	4	Every 24H	0.1	2	

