9.1.6 Guidelines for Discharge and Follow-up

Discharge: Subjects may be discharged from the hospital at the discretion of the treating attending physician, but the suggested discharge criteria are delineated in Appendix 3.

Medications: Any remaining doses of study medication, as outlined above, will be completed by mouth at home. Subjects will also complete any remaining doses of the 5-day course of azithromycin. Any additional antibiotic therapy can be chosen by the attending physician as deemed necessary for good subject care.

Follow-up: A follow-up appointment in the sickle cell clinic will be made for approximately 1 week after study enrollment and 1 month after discharge. At each visit a standardized interval history (between discharge and the follow-up visit) will be obtained for pain intensity, pain treatment, respiratory symptoms, and any inpatient or outpatient evaluation and management of SCD-related complications.

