Pain scale ⁴	X		Every 4h		X	X
Concomitant Medications	X	X	X	X	X	X
Opioids used (quantified)		X				
Pulse oximetry (record every 4 hrs)	X			X (q4h)	spot	spot
Fluid balance (ins and outs)			Every 8h			
Pregnancy test (if applicable)	X					
Study drug administration			Every 12- 24h			
Occurrence of AEs or SAEs				X	X	X
Number of transfusions	X	X			X	X
Pulmonary function testing						X
Compliance					X	X

¹Appendix 3.

²Includes pain history, pain treatment, respiratory symptoms, inpatient or outpatient evaluations and management of SCD-related complications (rebound VOC).

³Only if temperature $\geq 38.5^{\circ}\text{C}$ or at discretion of attending physician

⁴Oucher Scale (age <10 years) or numeric rating scale (age ≥ 10 years)

⁵**Vital signs recorded every 4 h and I/Os every 8 h on subject's medical record. Study personnel will collect the maximum values of the subject's vital signs every 24h.**

⁶**Follow-up #1 is after completion of study drug between days 7-10. Follow-up #2 is thirty days (+/- 3 days) after discharge from hospital and no more than 60 days after study enrollment**

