11 ADVERSE EVENTS

11.1 Safety Assessment Overview

Subjects will be evaluated every day while hospitalized. Subsequently, subjects will have 2 scheduled evaluations approximately 1 week after study enrollment and 1 month after discharge. At these follow-up visits, subjects and their parent(s) will be queried regarding recent medical events and/or procedures. Specific events will be documented to ascertain the nature and treatment of the event, including pain crises, episodes of acute chest syndrome, transfusions, and hospital admissions. These reportable events and diagnoses will be followed up by the nurse coordinator, who will review hospital charts, medical records, and office visit records for documentation in the follow-up visit forms in the case report form (CRF).

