Based on these preliminary findings, we anticipate that dexamethasone will decrease the LOS by 30 hours (compared to 33 hours for Bernini and 27 hours for Huh) and we will therefore power our tests to detect a 30-hour difference. The data from Huh et al (2004)⁴⁸ gives evidence that the LOS for ACS may have a lognormal distribution, but the clinical hypothesis makes a statement about differences in mean of LOS not the natural log of LOS. Assuming the LOS in each treatment group is distributed as lognormal, normal distribution based statistical analysis methodologies can be used for analysis of the natural log of LOS. With the lognormal assumption, the mean LOS for each treatment group is a function of both the mean and variance of the natural log of LOS, so the following sample size calculations had to consider possible lognormal distributions and the mean difference on the untransformed scale.

Table 13.2 presents the lognormal transformed results of Table 13.1, which we used in the sample size calculations.

Table 13.2 Effect of dexamethasone on natural log of the duration of hospitalization for ACS in children

	Bernini et al, (1998) Ln(Duration of hospitalization)	Huh et al (2004) Ln(Duration of hospitalization)
Placebo	4.217 (SD=0.574)	4.216 (SD=0.707)
Dexamethasone	3.795 (SD=0.331)	3.954 (SD=0.560)

The hypothesis tested is: shortened duration of ACS signs and symptoms/hospitalization by at least 30 hours for children with SCD who are hospitalized for the treatment of ACS and receive dexamethasone. Using LOS as a surrogate, we used a two group Satterthwaite t-test of equal means (unequal variances, equal n's) to test the difference in natural log of the hospitalization duration between treatment groups. We additionally

assumed a two-sided alpha of 0.05 and 90% power. Several scenarios were explored in which we varied the lognormal variance parameter and lognormal mean parameter for the two treatment groups according to the ranges found in the two pilot studies.

If we assume that

- we are testing a two-sided hypothesis,
- the treatment effects seen in children are the same in adults,
- the lognormal population standard deviation for the placebo group is 0.6,
- the lognormal population standard deviation of the dexamethasone group is 0.3,
- the lognormal mean of the placebo group is 4.25,
- the lognormal mean of the dexamethasone group 3.95, (corresponding to a mean difference in LOS between the two treatment groups of 30 hours),

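### SAE collection runs to 30 days after the last dose, but the last scheduled contact is timed from discharge and, for most subjects with short stays, comes several days before that window closes

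*Protocol*

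**What the plan says.** Section 11.6.1 sets the SAE period: "SAE reporting will begin with events that arise after the informed consent is signed until 30 days after the last dose of study drug". The last scheduled visit has a different anchor. Footnote 6 of Table 10.2 (section 10.3.2) reads "Follow-up #2 is thirty days (+/- 3 days) after discharge from hospital and no more than 60 days after study enrollment". Section 11.1 agrees with the footnote: "subjects will have 2 scheduled evaluations approximately 1 week after study enrollment and 1 month after discharge". Section 9.1.6 also counts the second visit from discharge.

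The end of treatment is not tied to discharge. Under section 9.1.1 the 12-hourly phase "is given for a total of 2 days (4 doses) or until hospital discharge, whichever occurs first". Section 7.1.2 adds that "the study drug will be tapered over 6 days for a total duration of therapy not to exceed 8 days". Section 9.1.6 provides for the rest of the course after discharge: "Any remaining doses of study medication, as outlined above, will be completed by mouth at home".

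Adverse events, transfusions and admissions since discharge are asked about at the follow-up visits (sections 10.3.3 and 11.1). Compliance calls by the study nurse end with the regimen (section 9.4). No contact is scheduled after Follow-up #2. SAE reporting itself is triggered when the investigator learns of an event, not by a visit (section 11.6.1).

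**The concern.** The SAE window and the last visit both last about 30 days, but they start from different events. When discharge comes before the last dose, the visit on its target date comes before the window closes by the same interval. An SAE in those final days is found only if someone tells the site. The protocol therefore states an ascertainment period that its schedule does not actively cover to the end.

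The anchor is also an outcome the drug is expected to move, since section 13.4 plans on a stay 30 hours shorter with dexamethasone. The quarterly SAE tables in section 11.6.3 count subjects with an event, yes or no, without adjusting for time observed, and raise an alert only if the active arm is higher. If the stays differ as planned, the active arm is asked about a slightly shorter period from first dose.

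**Working it through.** **Inputs.** Table 9.1 (course); section 11.6.1 (window); Table 10.2 footnote 6 (visit); section 13.4 planning values for the natural log of stay in hours: placebo mean 4.25, SD 0.6; "the lognormal mean of the dexamethasone group 3.95", SD 0.3. Assumptions: stay is counted from the first dose, the full course is taken, and the first taper dose falls 12 or 24 hours after the fourth dose (shown as a range).

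**Reproducing the plan's figures.**
- Course: 2 + 2 + 2 + 2 = 8 days, as stated.
- Mean stays: exp(4.25 + 0.6²/2) = 83.9 h and exp(3.95 + 0.3²/2) = 54.3 h. The difference is 29.6 h (stated: 30 h).
- A two-group Satterthwaite t-test at two-sided 0.05 and 90% power gives 54 per group, as stated.

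**End of the window.** The four high doses fall at 0, 12, 24 and 36 h. Six daily taper doses starting at 48 h end on day 7.0; starting at 60 h they end on day 7.5. The window then closes on day 37.0 or 37.5, or earlier for stays under 36 h.

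**Gap.** Let v be the visit's deviation from target, −3 to +3 days.

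Gap = (last dose + 30) − (discharge + 30 + v) = last dose − discharge − v.

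For a full course the gap is positive if the stay is under 7.0–7.5 days (v = 0) or under 4.0–4.5 days (v = +3).

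**Share last seen before the window closes,** Φ((ln threshold in hours − mean)/SD):
- Placebo, v = 0: thresholds of 168 and 180 h give z = 1.46 and 1.57, so 93–94%.
- Dexamethasone, v = 0: z is about 3.9 or more, so about 100%.
- Placebo, v = +3: thresholds of 96 and 108 h give z = 0.52 and 0.72, so 70–76%.
- Dexamethasone, v = +3: z = 2.05 and 2.44, so 98–99%.
- v = −3: about 98% and 100%.

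**Size of the gap at v = 0** (1,000,000 simulated stays per arm). The mean is 4.7–5.2 days on dexamethasone. On placebo it is 3.4–3.9 days as a signed mean, or 3.6–4.1 days with negative gaps set to zero. The arms differ by 1.1–1.3 days, in line with 29.6/24 = 1.2. At the pilot mean stays in Table 13.1 the gap is 5.0–5.5 v 3.7–4.2 days (first pilot) and 4.5–5.0 v 3.4–3.9 days (second).

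**Longer stays.** Section 5 puts the mean ACS stay for all patients at about 7 days, with children about 3 days shorter than adults. Assuming adult mean stays of 7 to 9 days and log SD 0.6, 45–66% are last seen early at v = 0 and 15–33% at v = +3. The mean signed gap then runs from +0.5 to −2.0 days. Section 7.1.2 anticipates at most 56 adults beside up to 112 children.

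**The case against.** The strongest reply is that SAE reporting does not stop at the last visit. Section 11.6.1 obliges the investigator to report within a day of learning of an event, and follow-up takes place in the subject's own sickle cell clinic. This stands: what is missing is a scheduled query in the last few days, not the duty or the means to report.

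The second reply concerns who is affected. A reader might infer that nearly every subject in the trial is last seen too early. The documents do not support that. The planning stays come from paediatric pilots; adults may stay 7 days or longer; about a quarter to 30% of placebo subjects seen at +3 days have no gap; and subjects who stop early, or start the taper early for leukocytosis (section 9.1.2), have an earlier last dose and so a smaller gap or none.

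Third, a reader might infer that the gap is inherently larger on dexamethasone and biases the safety comparison. It is larger only if dexamethasone shortens the stay, which is the hypothesis under test; with equal stays the gap is equal. Even on the planning values the difference is about 1.2 days in a window of about 37. The documents give no event rate for those days from which to estimate an effect on any test.

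Fourth, the late harm of most interest, rebound vaso-occlusive admission, is counted over the week after discharge (section 10.3.3). A visit 27 to 33 days after discharge covers that week fully in both arms, so no loss can be inferred there. Nor do the documents support a material bias in the one-month radiograph and pulmonary function results: a 1.2-day shift is smaller than the allowed plus or minus 3 days.

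Finally, a discharge anchor has a merit: both arms get the same time at risk of readmission. The fix has to respect this.

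**Conclusion.** The mismatch is real and does not depend on the drug working. With both arms at the planned placebo stay, the mean gap at the target visit would still be about 3.4 to 4.1 days in each. On the paediatric planning stays, 93–100% of subjects seen on the target day and 70–99% of those seen at +3 days are last actively questioned before the stated SAE window closes. The visit tolerance does not cure this.

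The consequence is modest: the last few days of a window of about 37 days rest on spontaneous reports. The between-arm difference of about 1.2 days is conditional on efficacy and small.

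The figures assume a full course and planning stays counted from the first dose. They shrink for longer stays and early stopping. The stated window covers SAEs only; section 11.6.1 gives no matching end date for non-serious events, so no shortfall is claimed for those. This is an inexpensive alignment of the schedule with the protocol's own commitment, not a threat to the primary analysis. Sample size and alpha are unaffected.

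**What to change.** Reconcile sections 9.1.6, 10.3.2 (Table 10.2, footnote 6), 10.3.3, 11.1 and 11.6.1 so that the closing SAE and readmission query falls at or after 30 days from the last scheduled dose in both arms. Either route works:

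1. Time Follow-up #2 from the first dose, for example days 38 to 44. This is after closure at day 37.0–37.5. Since enrollment and randomization must fall within 24 hours of diagnosis and the first dose within 2 hours of randomization, day 44 is at most about day 45 from enrollment, inside the 60-day limit.
2. Keep the discharge-anchored visit and add one closing SAE phone query in that same period.

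**Cost.** Route 1 adds no visit but needs edits to these sections and the consent wording. The planned visit now falls on average at day 32.3 (dexamethasone: 54.3/24 + 30) or 33.5 (placebo: 83.9/24 + 30). A visit between days 38 and 44 is therefore roughly 5 to 10 days later, with possibly slightly more missed visits. Post-discharge time would also differ between arms if stays differ: at day 41, 41 − 2.3 = 38.7 days on dexamethasone and 41 − 3.5 = 37.5 on placebo. Readmissions should therefore also be reported over a fixed post-discharge interval, as the one-week rebound endpoint already is. Route 2 leaves the visit and its radiograph and lung function tests where they are, and costs one call per subject.

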11.6.2 Reporting of All Serious Safety Concerns

Serious safety issues that arise in this study will be brought to the attention of the CSCC Data and Safety Monitoring Board (DSMB), which will make recommendations to the National Heart, Lung, and Blood Institute (NHLBI) regarding possible suspension or termination of the study. The NHLBI will consider the DSMB's recommendations, determine an appropriate action and notify the Principal Investigator (PI) and the CSCC Statistics and Data Management Center (SDMC). The PI will notify all participating investigators, who will implement the actions directed by NHLBI. This section defines "serious safety issues" and describes procedures for bringing them to the attention of the DSMB.

The SDMC or PI will make the following types of reports that can alert the DSMB to a potential safety issue:

- Ad hoc reports of fatal, life-threatening, or unexpected serious adverse events that are made within 7 or 15 calendar days, as specified in Section 11.7.1.
- Reports of quarterly statistical analyses of all serious adverse events. The SDMC makes such analyses quarterly, but files a report to the DSMB only when analyses indicate that a safety issue has arisen, as defined by the "alert" criteria.
- Reports of semi-annual SDMC analyses of all adverse events and of adverse clinical laboratory trends. These reports will highlight any safety issues revealed by the analyses that meet the "alert" criteria.

